	Relapse-free survival	Relapse-free survival is defined only for subjects who achieve CR or CRi and is measured as the interval from the date of first documented CR or CRi to the date of documented relapse, death from any cause, or lost to follow-up, whichever occurs first.
	Complete cytogenetic Response (CyCR)	Proportion of subjects with complete cytogenetic response (CyCR) based on modified IWG 2003 response criteria for AML (Appendix 17.3).

Table 2: Study Endpoints (Continued)

Endpoint	Name	Description
	Duration of response	Duration of response is defined as the time from the first documented CR/CRi to documented morphologic relapse, PD based on modified IWG 2003 response criteria for AML (Appendix 17.3) or death due to any cause, whichever occurs first.
	Hematologic Improvement Rate	Proportion of subjects achieving a hematological improvement (HI-N + HI-P + HI-E) according to IWG 2006 response criteria (Appendix 17.2).
Both Cohorts		
Secondary	Safety	Type, frequency, seriousness and severity of adverse events (AEs), and relationship of AEs to study treatment, clinical laboratory evaluations.
	Overall survival (OS)	Time from randomization to death due to any cause.
	One-year survival	The probability of survival at 1 year from randomization.
	PK	Durvalumab concentration.
CCI	[REDACTED]	[REDACTED]
	[REDACTED]	[REDACTED]
	[REDACTED]	[REDACTED]
	[REDACTED]	[REDACTED]
	[REDACTED]	[REDACTED]
	[REDACTED]	[REDACTED]
	[REDACTED]	[REDACTED]

[REDACTED] = hematological improvement; HI-E = hematological improvement – erythroid response; HI-NE = hematological improvement – neutrophil response; HI-p = hematological improvement – platelet response; IWG = International Working Group; mCR = marrow complete remission; OS = overall survival; PD = progressive disease; CCI [REDACTED] PK = pharmacokinetics; PR = partial remission.

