5.2. Analysis Populations

5.2.1. Intent to Treat Population

The intent to treat (ITT) Population will include all randomized subjects. The primary efficacy analyses will be performed on the ITT Population.

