10. EFFICACY ANALYSIS

All efficacy analyses will be carried out on the ITT Population. Supportive efficacy analyses will also be performed using EE Population.

All efficacy endpoints will be summarized by disease cohort and treatment arm.

All confidence intervals (CIs) will be provided at a level of 95% and between-group comparisons will be provided as appropriate as described below.

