The number and percentage of subjects who achieve each component of the overall response (CR, PR, mCR, HI-E, HI-P, HI-N) will be summarized together with associated two-sided 95% CI.

The best overall response per IWG 2006 response criteria will be summarized. The best overall response is defined as the best response prior to progressive disease and first subsequent therapy.

The below order will be considered for the definition of best response:

1. CR
2. PR
3. mCR
4. SD
5. PD
6. Disease transformation
7. Failure due to death
8. Not Evaluable/Missing

Acute Myeloid Leukemia Cohort

For the AML cohort, the primary efficacy endpoint is the proportion of subjects achieving an overall response rate (CR or CRi) based on modified IWG 2003 response criteria for AML ([Appendix 17.3](#)). The ORR will be summarized together with two-sided 95% CI. Subjects discontinued before 6-cycle treatment without achieving overall response will be counted as nonresponders.

The number and percentage of subjects who achieve CR, PR, CRi, HI-E, HI-P and HI-N will be summarized together with associated two-sided 95% CI

The best overall response per modified IWG response criteria will be summarized. The best overall response is defined as the best response prior to progressive disease and first subsequent therapy.

The below order will be considered for the definition of best response:

1. CR
2. CRi
3. CRc

4. PR
5. SD
6. PD
7. Treatment failure
8. Not Evaluable/Missing

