Duration of response will be calculated only for subjects who achieve CR, mCR, PR or HI for the MDS Cohort, CR or CRi for the AML Cohort. Duration of response is defined as the time from first response observed until relapse, PD or death. Duration of response will be censored at the last response assessment date that the subject is known to be progression-free for:

- Subjects who have not relapsed, progressed or died at the time of analysis.
- Subjects who have withdrawn consent or are lost to follow-up prior to documentation of progression.

Censoring rules are defined in [Table 4](#).

Duration of response will be analyzed using the KM method. Median duration of response along with two-sided 95% CI will be provided for each cohort and treatment group.

In addition, the duration of each specific subcategory of response in the MDS Cohort (CR, mCR, PR or HI) and in the AML Cohort (CR) will be summarized using standard descriptive statistics.

Relapse-free Survival (RFS)

Relapse-free survival is defined only for subjects who achieve CR or PR for MDS subjects, CR and CRi for AML subjects, and is measured as the interval from the date of first documented response to the date of disease relapse or death from any cause, whichever occurs first. Subjects who are still alive and relapse-free will be censored at the date of their last response assessment. The RFS curve will be estimated using KM method.

Median RFS along with two-sided 95% CI will be provided for each cohort and treatment group. The RFS at 6 and 12 months will be estimated and compared using Kaplan-Meier (KM) method.

Censoring rules are defined in [Table 4](#).

Cytogenetic Response

External central pathology/cytogenetic reviewers will review the morphologic/cytogenetic data from bone marrow aspirate (BMA), bone marrow biopsies (if performed) to determine whether a subject achieved a cytogenetic response (complete or partial cytogenetic responses for MDS subjects and cytogenetic complete response for AML subjects). For cytogenetic response evaluable subjects (ie subjects with baseline cytogenetic abnormalities), the number and percentage of subjects who achieve the cytogenetic responses will be summarized together with associated two-sided 95% CI.

MDS Cohort:

Progression-free Survival (PFS)

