Progression-free survival is calculated as the time from randomization to the first documented progression, relapse or death due to any cause during or after the treatment period, whichever occurs first. Subjects who are still alive and progression-free will be censored at the date of their last response assessment. The PFS curve will be estimated using KM method.

Median PFS along with two-sided 95% CI will be provided for each cohort and treatment group. The PFS at 6 and 12 months will be estimated and compared using Kaplan-Meier (KM) method.

A sensitivity analysis of PFS will be performed, censoring PFS at the time of subsequent systemic anticancer therapy if the subject did not progress before that time.

Transformation to AML and Time to AML Transformation

Number of subjects with transformation to AML and time to transformation to AML will be summarized. Time to transformation to AML is defined as the time from the date of randomization until the date the subject has documented transformation to AML (at least 30% of BM blats). Subjects who do not transform to AML will be censored at the date last disease assessment date. Median time to transformation to AML and associated two-sided 95% CI will be estimated using KM method.

AML Cohort:

HI

Rate of HI – erythroid response (HI-E), hematological improvement – platelet response (HI-P) and hematological improvement – neutrophil response (HI-N) according to IWG 2006 response criteria for MDS ([Appendix 17.2](#)), will be provided together with Wald asymptotic two-sided 95% CIs.

Table 4: Event and Censoring Rules for Progression-free Survival, Duration of Response, Time-to-Response and Relapse-free Survival

Situation	Date of Progression or Censoring	Situation Outcome
Censoring Rules for PFS and DoR		
Progression	If the first PD is a scheduled assessment then Date of first PD; If the first PD is an unscheduled assessment and no previous assessment, then Date of PD; If the first PD is an unscheduled assessment and has previous assessment, then Date of previous assessment (regardless of the response type).	Event
Death between scheduled assessments or within the first two missed scheduled assessments	Date of death	Event
No progression	Date of last adequate assessment with evidence of no PD	Censored
Death or progression after two or more missed scheduled assessments	Date of last adequate assessment with evidence of no PD; if no adequate assessment exists then censored at date of first dose	Censored

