Erythroid response (HI-E) (Pretreatment < 11 g/dL)	
 ▪ Hgb increase by \geq 1.5 g/dL in \geq 8 weeks 
OR
 
 ▪ Relevant reduction of units of RBC transfusions by an absolute number of at least 4 RBC transfusions/8 weeks compared with the pretreatment transfusion number in the previous 8 weeks. Only RBC transfusions given for a Hgb of \leq 9.0 g/dL pretreatment will count in the RBC transfusion evaluation 
 ▪ For Hgb, 7/3 rule should be applied first
Platelet response (HI-P) (Pretreatment < $100 \times 10^9/L$)	
 ▪ in \geq 8 weeks Absolute increase of $\geq 30 \times 10^9/L$ for patients starting with $> 20 \times 10^9/L$ 
OR
 
 ▪ Increase from $\leq 20 \times 10^9/L$ to $> 20 \times 10^9/L$ and by at least 100%

Neutrophil response (HI-N) (Pretreatment $< 1.0 \times 10^9/L$)	
 ▪ in ≥ 8 weeks At least 100% increase and an absolute increase from mean of pre-dose of $> 0.5 \times 10^9/L$
---	---

AML = acute myeloid leukemia; Hgb = hemoglobin; RBC = red blood cell

Source: Cheson BD, Greenberg PL, Bennett JM, Löwenberg B, Wijermans PW, Nimer SD, et al. Clinical application and proposal for modification of the International Working Group (IWG) response criteria in myelodysplasia. Blood. 2006; 108(2): 419-25.

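### HI-E, HI-P and HI-N rates are taken over all randomized subjects although only subjects below a pretreatment cut-off can score, which dilutes the rates and arm differences and costs some power

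*SAP*

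**What the plan says.** SAP section 10 sets the default: "All efficacy analyses will be carried out on the ITT Population". SAP 5.2.1 defines that population: "The intent to treat (ITT) Population will include all randomized subjects". The EE population, used for support, is not restricted by baseline counts either.

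HI appears in three places, none with a denominator of its own:
- SAP Table 2 (section 4.1) defines the AML secondary endpoint as a combined rate: "Proportion of subjects achieving a hematological improvement (HI-N + HI-P + HI-E".
- SAP 10.1 tabulates the lineages beside the primary endpoint. For AML: "The number and percentage of subjects who achieve CR, PR, CRi, HI-E, HI-P and HI-N will be summarized". A parallel sentence covers the MDS components.
- SAP 10.2 (AML cohort, HI) says the lineage rates "will be provided together with Wald asymptotic two-sided 95% CIs".

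SAP 17.2 attaches an entry condition to each lineage: "Erythroid response (HI-E) (Pretreatment < 11 g/dL" for the erythroid response, "Platelet response (HI-P) (Pretreatment <" 100 x10^9/L for platelets, and ANC below 1.0 x10^9/L for neutrophils. Protocol Appendix D carries the same conditions.

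For another response endpoint, SAP 10.2 does restrict the denominator: "For cytogenetic response evaluable subjects (ie subjects with baseline cytogenetic abnormalities".

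**The concern.** A subject who starts above a cut-off cannot register an improvement in that lineage whatever the treatment does. Such subjects can enrol. The protocol's eligibility criteria set an upper WBC limit and require no low count. The protocol also plans for these subjects: the azacitidine dose rules in 7.2.2.1 describe a group with ANC of at least 1.5 x10^9/L, all of whom are above the HI-N cut-off. In MDS, very poor cytogenetics (4 points) plus marrow blasts above 10% (3 points) gives 7, which is IPSS-R Very High with no points for counts. Zero points for platelets means at least 100 x10^9/L, so that subject cannot score HI-P.

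With the ITT denominator, a lineage rate is the product of two things: how many subjects were cytopenic at entry, and how often cytopenic subjects improved. Only the second reflects treatment. The HI rate is a named secondary endpoint in AML, and SAP 10.2 says response rates are compared between arms by the primary-endpoint method, so the test is affected as well as the display. The text also leaves room for two programmers to build different tables: one could follow section 10 literally, another could read the 17.2 conditions as implying an eligible-only denominator.

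**Working it through.** **Inputs from the documents.** AML cohort 110 subjects, 1:1, so 55 per arm (SAP 4.1, 4.3.2). Two-sided Wald test with unpooled variance (SAP 10.1), applied to response rates generally (SAP 10.2). Randomization balances only cytogenetic risk within disease cohort (SAP 4.2).

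**Inputs assumed.** f, the share of subjects below a cut-off, and r, the HI rate among them. The documents give neither, so ranges are shown.

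**Step 1: reproduce the plan's own figures.** n per arm = [p1(1−p1) + p2(1−p2)] × (z_0.975 + z_power)² / (p1−p2)².
- AML: (0.1875 + 0.2500) × (1.960 + 0.842)² / 0.25² = 54.9, so 55 per arm and 110 in total; power 0.800.
- MDS: (0.2304 + 0.2016) × (1.960 + 1.282)² / 0.36² = 35.02, so 36 per arm and 72 in total; power 0.908.

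The unpooled two-sided formula matches both cohorts, so it is used below.

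**Step 2: dilution.** ITT rate = f × r, and ITT difference = f × (r1 − r0). A 20-point difference among eligible subjects becomes 10 points at f = 0.5, 14 at f = 0.7 and 18 at f = 0.9.

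**Step 3: power.** Power = Φ(difference/SE − 1.96). On ITT, SE² = [f·r0(1−f·r0) + f·r1(1−f·r1)]/55. On eligible subjects, SE² = [r0(1−r0) + r1(1−r1)]/(55f).

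| f | 30% vs 60%: ITT rates | Power ITT | Power eligible | 20% vs 40%: ITT rates | Power ITT | Power eligible |
|---|---|---|---|---|---|---|
| 0.4 | 12% vs 24% | 38% | 55% | 8% vs 16% | 25% | 32% |
| 0.5 | 15% vs 30% | 48% | 65% | 10% vs 20% | 32% | 38% |
| 0.7 | 21% vs 42% | 68% | 79% | 14% vs 28% | 45% | 50% |
| 0.9 | 27% vs 54% | 85% | 88% | 18% vs 36% | 58% | 60% |

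The direction is general under this approximation. Squared z is 55f(r1−r0)² divided by [r0 + r1 − f(r0² + r1²)] on ITT, and by [r0 + r1 − (r0² + r1²)] on eligible subjects. For f below 1 the first divisor is larger, so the ITT test is weaker despite its larger n. The gap closes as f nears 1 and is smaller when response rates are low.

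**Step 4: chance imbalance in f.** The SD of the between-arm difference in eligible share is √(2f(1−f)/55), about 9 points for f of 0.4 to 0.7 and 6 points at 0.9. With no treatment effect and r = 30%, this moves the ITT HI difference by 0.30 × SD: 2.8, 2.9, 2.6 and 1.7 points at f = 0.4, 0.5, 0.7 and 0.9. The sampling SE of that difference is 6.2, 6.8, 7.8 and 8.5 points.

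**Step 5: type I error.** In 400,000 simulated trials per setting with no effect, rejection was 0.054 to 0.057 on ITT and 0.056 to 0.061 on eligible subjects (f of 0.5 to 0.8, r of 0.3 or 0.4).

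**The case against.** A reader might infer that the arms can be driven apart by baseline counts alone, so that the comparison is biased or its error rate inflated. The documents do not support that. Treatment is randomized, so imbalance in eligibility averages to zero. The Wald variance at rate f × r already contains the variation in eligibility, which is why step 5 shows no penalty for ITT relative to the alternative. Step 4 shows the imbalance is well inside ordinary sampling error, and SAP 7 and 7.2 already summarize baseline Hgb, platelets and ANC by arm.

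A reader might also infer that the cytogenetic denominator was restricted for this very reason. The SAP gives no reason; the passage shows only that an evaluable denominator was written for one endpoint and not for the other.

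The power loss depends on unsourced assumptions. At 20% versus 40% the gain is only about 2 to 7 points, and HI is an unpowered secondary endpoint. The combined AML rate is diluted no more than any single lineage, and probably less, because a subject below any one cut-off can score.

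An all-randomized percentage is also a legitimate, conservative summary of how many treated subjects improve, and deserves to stay. All of this limits the size of the point. None of it supplies the missing denominator.

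**Conclusion.** The point stands as a minor analysis and reporting improvement. As written, subjects who cannot score on a lineage count as failures, and each lineage rate and arm difference shrinks by the factor f. The power gain from an evaluable denominator runs from about 2 points (f = 0.9, 20% versus 40%) to about 17 points (f = 0.4 or 0.5, 30% versus 60%). These figures rest on assumed f and r, equal f in both arms, 55 per arm and the normal approximation. The ITT reading itself rests on the general rule in SAP section 10, since the HI paragraph names no population.

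The composite MDS primary ORR should stay on ITT; nothing here calls it into question.

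**What to change.** In SAP 10.1 (components, both cohorts) and 10.2 (AML HI):
- Report each lineage rate with its 95% CI on lineage-evaluable subjects, meaning those with a pretreatment value below the SAP 17.2 cut-off. Show n/N by arm, and keep the ITT percentage as a second column.
- For the combined AML HI rate in Table 2, use subjects below at least one cut-off.
- Define eligibility with the same baseline value that the response derivation uses: for Hgb, the value passing the 7/3-day rule in SAP 5.3.4; for ANC, the pre-dose mean named in 17.2.
- Count as HI-E evaluable any subject who can score by the transfusion-reduction route, even if no qualifying Hgb exists.
- Apply the SAP 10.2 between-arm comparison to the evaluable denominator for the AML HI secondary endpoint only. Add no new tests for the MDS components.

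Eligibility is fixed before treatment, so the randomized comparison is kept. The data are already collected. The cost is SAP wording, these derivation rules and an extra column; the small downside is a smaller denominator per lineage.

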5.1.1. Dates Handling

Dates will be stored as numeric variables in the SAS analysis files and reported in DDMMYYYY format (ie, the Date9 datetime format in SAS). Dates in the clinical database are classified into the categories of procedure dates, log dates, milestone dates, outcome dates, and special dates.

- **Procedure Dates** are the dates on which given protocol-specified procedure are performed. They include the dates of laboratory testing, physical examinations, bone marrow aspirates or biopsies, etc. They should be present whenever data for a protocol-specified procedure is present and should only be missing when a procedure is marked as NOT DONE in the database. Procedure dates will not be imputed.
- **Log Dates** are dates recorded in the case report form (CRF) data logs. Specifically, they are the start and end dates for adverse events and concomitant medications/procedures. They should not be missing unless an event or medication is marked as *ongoing* in the database. Otherwise, incomplete log dates will be imputed according to the rules in [Appendix 17.1](#) (eg, for duration or cycle assignment etc). However, in listings, log dates will be shown as recorded without imputation.
- **Milestone Dates** are dates of protocol milestones such as randomization, study drug start date, study termination, etc. They should not be missing if the milestone occurs for a subject. They will not be imputed.
- **Outcome Dates** are dates corresponding to study endpoints such as survival, progression, etc. In most cases they are derived either from a milestone (eg, the survival date is derived from the death date), or a procedure date (eg, the progression date is derived from the date of the tumor scan that was used to determine progression). They may be subject to endpoint-specific censoring rules if the outcome did not occur, but are not otherwise subject to imputation.

- **Special Dates** cannot be classified in any of the above categories and they include the date of birth. They may be subject to variable-specific censoring and imputation rules (see [Section 5.1.2](#) below).

Dates recorded in comment fields will not be imputed or reported in any specific format.

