Censoring Rules for RFS		
Relapse	If the first relapse is a scheduled assessment then Date of first relapse; If the first relapse is an unscheduled assessment and no previous assessment, then Date of relapse; If the first relapse is an unscheduled assessment and has previous assessment, then Date of previous assessment (regardless of the response type).	Event
Death between scheduled assessments or within the first two missed scheduled assessments	Date of death	Event
No relapse	Date of last adequate assessment with evidence of no relapse	Censored
Death or progression after two or more missed scheduled assessments	Date of last adequate assessment with evidence of no relapse; if no adequate assessment exists then censored at date of first dose	Censored
Censoring Rules for PFS (sensitivity analysis), DoR and RFS		
Additional therapy received prior to progression or death	Date of additional systemic anticancer therapy	Censored

Censoring Rules for TTR		
Subject responded before PD	First documented response date (CR, PR, mCr, or HI for mDS Cohort, CR or CRi for AML Cohort)	Event
Subject responded after PD	Date of last adequate disease assessment at PD date or death date	Censored
Other case	Date of last adequate disease assessment; if no adequate assessment exists, then censored at date of first dose	Censored

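### SAP Table 4 dates a progression or relapse found at an unscheduled assessment to the previous assessment, against the SAP's own PFS and RFS definitions and outcome-date rule

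*SAP*

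**What the plan says.** SAP Section 10.2, Table 4, gives three cases for a progression event in PFS and DoR. A first PD at a scheduled assessment takes its own date. A first PD at an unscheduled assessment with nothing before it also takes its own date. The third case is different: "If the first PD is an unscheduled assessment and has previous assessment, then Date of previous assessment (regardless of the response type". The RFS block repeats this for relapse: "If the first relapse is an unscheduled assessment and has previous assessment, then Date of previous assessment (regardless of the response type". Both rows have the outcome Event.

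Elsewhere the SAP says:
- PFS (Section 10.2, MDS cohort only) is "the time from randomization to the first documented progression, relapse or death due to any cause during or after the treatment period".
- RFS (Section 10.2) is "the interval from the date of first documented response to the date of disease relapse or death from any cause".
- Outcome dates (Section 5.1.1): as the worked example, "the progression date is derived from the date of the tumor scan that was used to determine progression"; and in general, "They may be subject to endpoint-specific censoring rules if the outcome did not occur, but are not otherwise subject to imputation".
- Landmarks (Section 10.2): "The PFS at 6 and 12 months will be estimated and compared using Kaplan-Meier (KM) method". RFS is treated the same way.
- Sensitivity analysis: "A sensitivity analysis of PFS will be performed, censoring PFS at the time of subsequent systemic anticancer therapy". This is the only one stated for PFS.

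SAP Section 15, which lists changes from the protocol's statistical section, does not mention the back-dating rule.

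**The concern.** If the unscheduled assessment is the first to show PD or relapse, the previous one by construction did not. Table 4 therefore records an event on a date when the subject was known to be free of it. The reported PFS, RFS and DoR would not be the quantities that the SAP defines. Some responders could have a DoR or RFS of 0 days, and events could move to the other side of the 6- or 12-month landmark. Two programmers could also derive different dates from the same data, one following Section 5.1.1 and the definitions, the other following Table 4.

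The rule is likely to be used. Protocol Table 3, footnote p, provides for marrow examinations off the three-cycle schedule when progression is suspected.

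**Working it through.** The documents state no PFS, DoR or RFS figure to reproduce. The check compares the texts, then sizes the date shift.

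**1. Texts side by side**
- The PFS definition ends at the first documented progression, relapse or death. Table 4 ends at an assessment that documented none of these.
- The RFS definition ends at the date of relapse. Table 4 ends at an assessment before it.
- Section 5.1.1 takes the progression date from the procedure that determined progression, and allows endpoint-specific censoring rules only where the outcome did not occur. Here it did occur.
- For AML DoR ended by PD, protocol Appendix K dates PD to the first date the criterion was seen. SAP Section 17.3 changes the AML PD criterion but sets no PD date.

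Table 4 is also inconsistent within itself. With no PD on Day 162, a death on Day 200 between scheduled assessments is an event on Day 200, but an unscheduled PD on Day 200 is an event on Day 162. An assessment showing no PD is a censoring date in the row for subjects without progression, and can be an event date in the progression row.

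**2. Shift per subject**

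Inputs: 28-day cycles; marrow on Day 22 of every third cycle (protocol Table 3); months = days / 30.4375 (SAP Section 5.1.2). I assume no cycle delays and first dose on the day of randomization.
- Marrow days: 2 × 28 + 22 = 78; 5 × 28 + 22 = 162; then 246, 330, 414.
- Maximum shift: just under 3 × 28 = 84 days. With one missed assessment it is just under 168, because Table 4 censors only after two or more. It is at most about 14 days if the Day 1 and Day 15 blood counts (from Cycle 3) count as assessments.
- AML example: CR on Day 78, unscheduled relapse on Day 134. Documented RFS = 134 − 78 = 56 days; Table 4 gives 78 − 78 = 0.
- MDS example: no PD on Day 162, unscheduled PD on Day 200. The 6-month mark is 6 × 30.4375 = 182.6 days. The documented event falls after it; the Table 4 event, on Day 162, falls before it.

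**3. Illustration at group level**

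The documents give neither the share of progressions found off schedule (u) nor a median PFS. I assume exponential times with median m months, no deaths and no censoring, so S(t) = 0.5^(t / (m × 30.4375)). At landmark t:
- documented dates: (1 − u) S(previous marrow) + u S(t)
- Table 4: (1 − u) S(previous marrow) + u S(next marrow)
- difference: u [S(t) − S(next marrow)]

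For m = 10 and t = 182.6: S(162) = 0.6915, S(182.6) = 0.6598, S(246) = 0.5711. With u = 0.20, documented dates give 0.80 × 0.6915 + 0.20 × 0.6598 = 0.6851, and Table 4 gives 0.80 × 0.6915 + 0.20 × 0.5711 = 0.6674.

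| Landmark | u | Documented | Table 4 | Difference (points) | True onset |
|---|---|---|---|---|---|
| 6 months | 0.05 | 69.0% | 68.5% | 0.4 | 66.0% |
| 6 months | 0.10 | 68.8% | 67.9% | 0.9 | 66.0% |
| 6 months | 0.20 | 68.5% | 66.7% | 1.8 | 66.0% |
| 6 months | 0.40 | 67.9% | 64.3% | 3.5 | 66.0% |
| 12 months | 0.20 | 46.4% | 45.5% | 0.9 | 43.5% |
| 12 months | 0.40 | 45.7% | 43.9% | 1.8 | 43.5% |

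Differences are taken before rounding. For u = 0.20-0.40, the 6-month difference is 2.1-4.3 points at m = 6 and 1.5-2.9 points at m = 14. If gaps are at most 14 days (m = 10), it is 0-0.8 points. A simulation of 400,000 subjects agrees with the 6-month values at u = 0.20 and 0.40 (m = 10), with a mean back-date of 40 days and a maximum of 84.

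**The case against.** The best defense is that Table 4 is the specific, deliberate rule: the definitions name the event and the table assigns its date. Section 5.1.1 is hedged (it describes most cases), its example is a scan that plays no part in response here, and its imputation language mainly concerns missing dates. The Appendix K date is narrow, since it belongs to a criterion that the SAP replaces. These points weaken the supporting conflicts but not the main one. If Table 4 governs, the reported endpoints do not match their definitions, and Section 15 does not say so.

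The defense on size is stronger, and most of it stands:
- Progression is observed only in intervals, so any date is a convention. In the model above Table 4 is nearer true onset at u = 0.20 (+0.8 v +2.5 points at 6 months) and at 12 months (+2.0 v +2.9 at u = 0.20; +0.4 v +2.2 at u = 0.40). At 6 months with u = 0.40 the errors are similar (−1.7 v +1.9).
- The model omits deaths, which Table 4 normally dates correctly. If 30-50% of first events were deaths with the same timing (an assumption), 1.8-3.5 points becomes about 0.9-2.5.
- The protocol requires a marrow at treatment discontinuation. If that counts as scheduled, the 5-10% case is more plausible.
- With about 36 subjects per MDS arm, the standard error of a 66% rate is √(0.66 × 0.34 / 36), about 8 points.
- Effect on the comparison is small: in a simulation with no treatment effect and 40% v 10% unscheduled detection, the hazard ratio moved from 1.078 to 1.087 (6-month median) or from 1.035 to 1.041 (12-month median).

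None of this makes Table 4 coherent. It moves only some events, leaves scheduled progressions and ordinary deaths at their own dates, and gives no reason.

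**Conclusion.** The concern holds: Table 4 is wrong as written, and should be fixed. The contradiction rests on the text alone. The per-subject shifts follow from the schedule, with no cycle delays assumed. The group-level figures are illustrative: they depend on an assumed unscheduled share, exponential times and no deaths, and they measure departure from the SAP's defined endpoint, not bias against true onset.

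The reach is limited to PFS (MDS), DoR and RFS, all secondary. ORR, OS, power and type I error are untouched. No shift in medians, between-arm bias or effect on the futility decision is claimed.

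**What to change.** In Table 4, replace the three conditions in the PFS/DoR progression row and in the RFS relapse row with one rule: the event date is that of the assessment that first documents PD (or relapse), whether scheduled or unscheduled. State that the same rule applies to relapse as an event in PFS and DoR, since the PFS/DoR row now mentions only PD. If a scheduled-visit dating convention is wanted, keep it as a named sensitivity analysis.

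The cost is a few lines in the SAP and a programming change. Data collection does not change.
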